A hierarchical stepwise backward elimination technique will be used to reduce the model. The two-way interactions will be reviewed first, the two-way interaction with the largest p-value provided that p-value is greater than 0.05 will be removed from the model and the model refit and repeated until only two-way interactions with p-values < 0.05 are retained. The main effects for any two-way interaction retained in the model must remain in the model as well as the randomized treatment. That being said, the main effects will be evaluated in the same manner as the two-way interactions. This analysis will be completed in the PP group as well.

9.10.2.3.4 *To estimate the proportion of subjects randomized to treatment with at least 50% improvement from baseline to 4 weeks in gravimetric sweat production (GSP)*

Subjects Included in Analysis: All FAS subjects randomized to receive the N-SWEAT patch.

Endpoint(s): The average of 2 accurate GSP measurements will be conducted for each Axilla at each time point. The total sweat production at each timepoint will be calculated by summing the average sweat production from both axilla. The percentage change at 4 weeks will be calculated based on the total sweat production at baseline and 4 weeks.

CANDESANT BIOMEDICAL	CLINICAL STUDY PROTOCOL SAHARA STUDY	Document #: CB-CLP-001 Revision: E
-------------------------	---	---------------------------------------

Statistical Analysis: The potential confounding factors of room temperature, position during evaluation and time of evaluation will be summarized for baseline and 4 weeks. The difference in temperature, time of evaluation and whether or not the baseline and 4 week evaluation were performed in the same or different position will be summarized. These factors will be evaluated with respect to their relationship with the endpoint and association with outlying values, if any, using graphical techniques and summary statistics. Depending on this evaluation, outlying values may be excluded from the analysis with justification provided and relationships, if any found, will be summarized.

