APPENDIX D: GSP INSTRUCTIONS

Materials Required

- Quantitative Filter Papers, 90 mm
- Room temperature environment (26°C-30°C recommended). Actual room temperature must be documented to ensure that the same temperature is applied for each gravimetric test.

Procedure

GSP should be measured at screening, baseline (~72 hours later) and at the 4-week follow-up visit. Measurements should be performed in the same position(s) (sitting, standing, or walking) at every visit. The position used should be document in the subject records. If the screening GSP Measurement and the Baseline GSP Measurement differ by more than 100%, the subject should not be enrolled. GSP should not exceed 300 mg/5 min in either axilla at either screening or baseline

IMPORTANT: Each gravimetric measurement must be taken in similar room conditions (same humidity and temperature as baseline). Whenever possible all Gravimetric tests for this study (screening, baseline and 4-weeks) should be taken at the same time of day (± 3 hours).

A minimum of two (2) measurements should be taken in each axilla at every timepoint to ensure accuracy of results. If following the 2nd readings there is concern regarding the measurement accuracy, a 3rd reading may be performed. An average of accurate reading(s) will be reported.

- Weigh the plastic tube (vial) with filter paper to be used for the assessment (in milligrams) and document the baseline combined weight of the filter paper and vial.
- Dry the subject's axilla with an absorbent tissue or similar. Allow subject to sit for 15 minutes at room temperature (20-25.6°C)
- Determine the planned treatment area and desired location for filter paper placement. Paper should be placed centrally, just under the axilla crease formed when arms are down by their side.
- Place the previously weighed filter paper in the subject's armpit and ask them to hold it there for 5 minutes.

Following the 5-minute application of the filter paper, the filter paper and vial together will be weighed again. The result is the difference in the weight from baseline filter paper and vial weight and post filter paper application (paper placed in vial and weighed). The difference is calculated in milligrams and recorded as mg/5mins.

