2. STUDY DESIGN, RANDOMIZATION AND BLINDING

The Sahara Study is a prospective, multi-center, randomized, blinded, pivotal study to evaluate the safety and effectiveness of the N-SWEAT Patch.

Subjects with primary axillary hyperhidrosis or excessive sweating (defined by a score of 3 or 4 on the HDSS), who have provided informed consent and have met the study eligibility criteria, will participate. Up to 120 adult subjects will be enrolled. The first 10 subjects will be treated with the N-SWEAT patch and constitute the roll-in cohort and up to 110 subjects will be randomized to 1 of 2 treatment groups in a 1:1 ratio to receive a single administration of the N-SWEAT Patch or a sham control patch. The randomization will be blocked by investigational center and stratified by HDSS 3 vs. 4 at baseline. Although a sample size of 100 subjects (50 in each group) is the target; up to 10 additional subjects may be enrolled to account for loss to follow up or other missing and critical data.

Randomized subjects will be blinded to their treatment assignment. Site personnel administering the treatment will observe the treatment effect and the disposal process and may be unblinded as a result of their observations. This person will not conduct the follow-up assessments and will not reveal the assumed treatment assignment to the subject, other site personnel, or the investigator at any time during the study follow-up period. Study subjects and study staff will be instructed not to discuss assumptions about the treatment received.

The sponsor will identify those who need to be unblinded in order to conduct the study. All others at the sponsor will remain blinded until the 4 week analysis.

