7. TIMING OF ANALYSES

Safety for the Roll-in cohort will be summarized when at least 2 weeks of follow-up is available on the last enrolled roll-in subject.

After the 30th, 60th, and 90th subject from the randomized cohort (active and control) is treated and followed for 7 days, the running safety report will be submitted to FDA. The report will be submitted within 30 days of treatment.

The interval safety report will include:

1. Cumulative frequency tables of all AE reported to date for the active patch, and all the AE reported to date for the sham patch, using the terminology in Table 9 in the investigational plan; and
2. A list of AEs in the recently completed 30-subject cohort, to include the device used (active or control), time to onset, time to resolution, intervention (including OTC product use), whether the AE was procedure- or device-related, and descriptive and photographic data.

Once all subjects complete 4 weeks of follow-up, the data will be summarized for evaluation of the endpoints. At this time, the sponsor will be unblinded to the treatment groups, but the investigators and subjects will remain blinded until study completion. Lastly, the data will be summarized when all subjects complete the study.

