A hierarchical stepwise backward elimination technique will be used to reduce the model. The two-way interactions will be reviewed first, the two-way interaction with the largest p-value provided that p-value is greater than 0.05 will be removed from the model and the model refit and repeated until only two-way interactions with p-values < 0.05 are retained. The main effects for any two-way interaction retained in the model must remain in the model as well as the randomized treatment. That being said, the main effects will be evaluated in the same manner as the two-way interactions. This analysis will be completed in the PP group as well.

11.2.3.4 To estimate the proportion of subjects randomized to treatment with at least 50% improvement from baseline to 4 weeks in gravimetric sweat production (GSP)

Subjects Included in Analysis: All FAS subjects randomized to receive the N-SWEAT patch.

Endpoint(s): The average of 2 accurate GSP measurements will be conducted for each Axilla at each time point. The total sweat production at each timepoint will be calculated by summing the average sweat production from both axilla. The percentage change at 4 weeks will be calculated based on the total sweat production at baseline and 4 weeks.

Statistical Analysis: The potential confounding factors of room temperature, room humidity , position during evaluation and time of evaluation will be summarized for baseline and 4 weeks. The difference in temperature, humidity, time of evaluation and whether or not the baseline and 4 week evaluation were performed in the same or different position will be summarized. These factors will be evaluated with respect to their relationship with the endpoint and association with outlying values, if any, using graphical techniques and summary statistics. Depending on this evaluation, outlying values may be excluded from the analysis with justification provided and relationships, if any found, will be summarized.

The proportion of patients with 50% or greater improvement from baseline to 4 weeks will be statistically compared to zero by calculating the Wilson's 95% two-sided confidence interval and comparing the lower bound to zero. If the lower bound is greater than zero, there is statistically

significant evidence that the proportion of subjects with a clinically relevant improvement exists and is greater than 0. This analysis will be completed in the PP population as well.

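### Outlying GSP values may be dropped from the main responder analysis after the endpoint has been examined, with no stated rule, and this tends to raise the reported rate

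*SAP*

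**What the plan says.** SAP 11.2.3.4 first summarises room temperature, humidity, position and time of evaluation at baseline and 4 weeks. It continues: "These factors will be evaluated with respect to their relationship with the endpoint and association with outlying values, if any". The tools for this review are graphs and descriptive summaries, with no numeric rule. Depending on what is seen, "outlying values may be excluded from the analysis with justification provided". Protocol 9.10.2.3.4 has the same rule without humidity in its list of factors: "Depending on this evaluation, outlying values may be excluded from the analysis with justification provided".

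The analysis covers only subjects randomized to N-SWEAT. The responder proportion is reported with a Wilson 95% interval, and success means a lower bound above zero. SAP 11.2.2 expects a rate of at least 50%. SAP 11.2.1 makes the ordered secondary endpoints candidates for labelling, with p-values and confidence intervals, if the sequence reaches them.

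On timing, SAP 7 says of the 4-week analysis: "At this time, the sponsor will be unblinded to the treatment groups, but the investigators and subjects will remain blinded until study completion". It does not say whether the outlier review comes before or after that step.

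SAP 6.5 treats another kind of exclusion differently. Major protocol violations for the per-protocol set are identified by the DSMB or an independent reviewer before the database is locked and the codes are opened. No such safeguard is given for GSP values.

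**The concern.** The exclusion applies to the main analysis, and the review that leads to it looks at the endpoint. A justification written after the endpoint has been seen makes the choice visible, but it does not make it pre-specified. Four things are missing: a definition of an outlier, a person who decides, a deadline before lock, and a required result with every value kept.

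There is also little statistical need for the rule. The endpoint is a yes/no classification, so a subject whose sweat production triples counts as one non-responder, the same as a subject with no change. An extreme value gets no extra weight, and removing it only takes a subject out of the denominator.

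At stake are the reported GSP response rate and its interval. Because a single responder passes the test against zero, these are the informative content of the endpoint. It has no sham comparison, so a shift in the rate is not offset by a similar shift in a control arm.

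**Working it through.** **Inputs from the documents.** 50 evaluable subjects per arm (SAP 4 and 11.1), with no separate sample size for GSP. Expected GSP response of at least 50% (SAP 11.2.2, item 4). Wilson 95% two-sided interval, lower bound compared with zero (SAP 11.2.3.4). GSP capped at 300 mg/5 min per axilla at screening and baseline (exclusion E-3), with no cap at 4 weeks.

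**Not in the documents, so assumed.** The number of exclusions, the outlier rule, the scale on which outliers are judged, and the distribution of GSP change.

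**Step 1: the planned denominator.** With n = [z(0.975)·√(2p̄q̄) + z(0.80)·√(p1q1 + p2q2)]² / (p1 − p2)²:
- 85% vs 60%: [1.960·√0.39875 + 0.842·√0.3675]² / 0.25² = 48.9, so 49 (stated 50; power at 50 per arm is 80.9%).
- 73% vs 44%: [1.960·√0.48555 + 0.842·√0.4435]² / 0.29² = 44.1, so 45 (stated 45).

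The stated sizes are reproduced to within one subject, and 50 is used below.

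**Step 2: the interval.** Wilson limits are [p + z²/2n ± z·√(p(1−p)/n + z²/4n²)] / (1 + z²/n), with z = 1.96. For 25/50 the centre is 0.500 and the half-width 0.134, giving 36.6% to 63.4%.

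**Step 3: remove k non-responders from 25/50.** The rate becomes 25/(50 − k).

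| k | Rate | Wilson 95% |
|---|---|---|
| 0 | 25/50 = 50.0% | 36.6% to 63.4% |
| 1 | 25/49 = 51.0% | 37.5% to 64.4% |
| 3 | 25/47 = 53.2% | 39.2% to 66.7% |
| 5 | 25/45 = 55.6% | 41.2% to 69.1% |
| 10 | 25/40 = 62.5% | 47.0% to 75.8% |

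Removing responders works the other way: 22/47 = 46.8% for three and 20/45 = 44.4% for five. The direction therefore depends on where outliers fall.

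**Step 4: where outliers fall.** Improvement is bounded at 100% and worsening is unbounded. Eligibility also limits baseline values from above, while 4-week values have no limit. On the percentage-change scale the long tail is therefore on the worsening side, among non-responders.

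**Step 5: a mechanical rule with no selective intent.** Let R be the 4-week total divided by the baseline total, log-normal with median m and log-SD s, and a responder if R ≤ 0.5. Exclude values of R beyond the quartiles by more than 1.5 x IQR. With n = 50 and 20,000 simulated trials:

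| m | s | Mean excluded | Rate, all values | Rate after exclusion |
|---|---|---|---|---|
| 0.5 | 0.5 | 2.1 | 50.0% | 52.2% |
| 0.5 | 0.7 | 2.8 | 49.9% | 53.1% |
| 0.5 | 1.0 | 4.0 | 50.0% | 54.4% |
| 0.6 | 0.7 | 2.8 | 39.6% | 42.1% |
| 0.7 | 0.7 | 2.8 | 31.5% | 33.5% |

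Almost every excluded subject is a non-responder; the mean number of responders excluded is at most 0.0013 per trial.

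**Step 6: the formal test.** For 0/50 the lower bound is 0; for 1/50 it is 0.35%. One responder is enough, with or without exclusions.

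**The case against.** The best defence is that SAP 11.2.3.4 starts from measurement conditions, not from response. It requires a justification and says that relationships found will be reported, so exclusions would be disclosed. Nothing in it says that values are dropped because of response status. Non-comparable conditions are also a real problem: Appendix D itself gives two room-temperature ranges (26 to 30°C and 20 to 25.6°C). All of this stands. It supports a rule for invalid readings based on conditions, but not a review that also uses the endpoint and sets no rule.

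The size is modest. A shift of 2 to 4 points is small beside a Wilson half-width of about 13 points, and the endpoint is reached only after the primary and three secondaries succeed. That stands too.

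A reader might infer several stronger things that the documents do not support:
- **That exclusions could turn failure into success.** Step 6 shows that dropping non-responders cannot change the test result. The 50% in SAP 11.2.2 is an expectation, so reaching it crosses no boundary.
- **That outliers will be chosen by an unblinded sponsor.** SAP 7 does not fix the order of review and unblinding. For a single-arm proportion the bias comes from seeing response, and the arm is known from the analysis set in any case.
- **That Appendix D already deals with the problem.** Its provision, "If following the 2nd readings there is concern regarding the measurement accuracy, a 3rd reading may be performed", covers doubtful accuracy within one visit. It cannot correct a difference in temperature or position between baseline and week 4.
- **That the composites and the GSP mean change are affected.** SAP 11.3.2 and 11.3.3 refer back to 11.2.3.4 for the calculation of percentage change, and 11.3.5 has its own text. None says whether exclusions carry over.

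**Conclusion.** The point holds as a weakness in how the GSP response rate would be estimated and reported. The plan permits discretionary exclusion from the main analysis after the endpoint has been examined, without the safeguard it applies to per-protocol exclusions.

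Under the assumptions of step 5 with a true rate of 50%, a mechanical rule raises the rate by 2.2 to 4.4 points. Five non-responder exclusions would add 5.6 points, but that number is only an illustration. The upward direction assumes that outliers are judged on percentage change or the untransformed ratio. On a log scale, with the symmetric distribution assumed and a median ratio of 0.5, exclusions would fall equally on both sides. The plan does not state the scale, which is part of the gap.

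Statistical success on this endpoint and the primary conclusion are untouched. The change is worth making because the rate and interval may be used in labelling and the remedy is cheap.

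**What to change.** Amend SAP 11.2.3.4 before data lock:

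1. The FAS result with all recorded GSP values is the main result and the one offered for labelling.
2. A reading may be invalidated only for a measurement fault documented at the visit, or on measurement conditions alone, by a named reviewer who sees neither arm nor GSP outcome and decides before data lock.
3. Any result that excludes outliers is a sensitivity analysis only, with the outlier definition and scale stated in advance and the number excluded shown by response status.
4. The same rule applies to SAP 11.3.2, 11.3.3 and 11.3.5.

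The cost is a few sentences and one sensitivity table, with no change to sample size, visits or data collection. Keeping all values does not widen the interval in the example: 25/50 spans 26.8 points (63.4 − 36.6) and 25/45 spans 27.9 (69.1 − 41.2). The sponsor gives up only a reported rate that might have been slightly more favourable.

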The proportion of patients with 50% or greater improvement in percentage change from baseline to 4 weeks will be statistically compared to zero by calculating the Wilson's 95% two-sided confidence interval and comparing the lower bound to zero. If the lower bound is greater than zero, there is statistically significant evidence that the proportion of subjects with a clinically relevant improvement exists and is greater than 0. This analysis will be completed in the PP population as well.

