11.2 Secondary Efficacy

11.2.1 Type I Error Control, Additional Claims and Labeling

Should the primary effectiveness endpoint be found to be statistically significant, additional secondary endpoints will be evaluated for inclusion in the labeling for the device including p-values and 95% confidence intervals. The secondary endpoints are listed in priority order in **Section 11.2.2** Priority Order and Hypothesis Tests and will be evaluated in that order. If statistical significance is achieved for the highest priority endpoint the testing will

move to the next highest until either statistical significance is not reached, or the list has ended. This ordered hypothesis approach permits each hypothesis to be evaluated at two sided $\alpha=0.05$ or equivalently one-sided $\alpha=0.025$ and controls the study-wide Type I error at 5%.

Secondary endpoints or additional analysis outside of those that do support additional claims are supportive in nature and not intended to support additional claims. Data may be included in labelling per agreement with the FDA and will be limited to summary statistics (e.g. mean, standard deviation, minimum, median, maximum, number and percent) and will not include 95% confidence intervals or p-values. For more information about the secondary endpoint analyses see **Section 11.2.3 Secondary Objectives**.

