Success is defined as a statistically significant difference (at the 0.05 two-sided significance level) between proportions of patients with at least 2 grade improvement in HDSS from baseline to 4 weeks between randomized group using CMH test stratified by baseline HDSS (3 vs. 4).

4. **Proportion of subjects with at least 50% improvement in gravimetric sweat production (GSP) in subjects treated with the N-SWEAT Patch only at 4-weeks. (GSP will be calculated based on the total sweat produced by both axillae.)**

H_0 : The proportion of subjects with at least 50% improvement in gravimetric sweat production (GSP) in subjects randomized to treatment (p_T) is not statistically significantly different from 0, $p_T = 0$.

H_a : The proportion of subjects with at least 50% improvement in gravimetric sweat production (GSP) in subjects randomized to treatment (p_T) is statistically significantly different from 0, $p_T \neq 0$.

Success is defined as a statistically significant result (at the 0.05 two-sided significance level). It is expected that at least 50% of subjects will have at least 50% improvement in gravimetric sweat production from baseline at 4-weeks.

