11.3 Observational Endpoints

Observational endpoints will be summarized at all available time points at the time of analysis. Observational endpoints are supportive in nature and not intended to support additional claims. Data may be included in labelling per agreement with the FDA and will be limited to summary statistics (e.g. mean, standard deviation, minimum, median, maximum, number and percent) and will not include 95% confidence intervals or p-values. Statistical significance will be determined based on a two-sided p-value of 0.05. The p-values for the observational endpoints will not be adjusted for multiplicity and should be interpreted with caution.

11.3.1 To compare the mean improvement over baseline for QoL-7 between subjects randomized to treatment as compared to sham

Subjects Included in Analysis: All FAS subjects will be included in the analysis.

Endpoint(s): QoL-7 score. The score is calculated by assigning 1 for a yes response and 0 for a no response and summing over the 7 questions.

Statistical Analysis: An analysis will be performed using all available time points with complete follow-up at the time of the analysis. A generalized linear mixed model be used to compare average change in QoL-7 from baseline to follow-up between randomized groups over time on study. The dependent variable change in QoL-7 from baseline to follow-up with independent variables to include randomized group, follow-up time, baseline HDSS and two-way interaction terms. The covariance structure among the compound symmetric, auto-regressive and unstructured that provides the best model fit by the Schwarz BIC criterion will be chosen.

A hierarchical stepwise backward elimination technique will be used to reduce the model. The two-way interactions will be reviewed first, the two-way interaction with the largest p-value provided that p-value is greater than 0.05 will be removed from the model and the model refit and repeated until only two-way interactions with p-values < 0.05 are retained. The main effects for any two-way interaction retained in the model must remain in the model as well as the randomized treatment. That being said, the main effects will be evaluated in the same manner as the two-way interaction terms.

This analysis will be repeated for each of the 7 questions that comprise the QOL-7 and in the PP population.

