11.3.2 To compare the proportion of patients with HDSS 1 or 2 at 4 weeks AND at least 50% improvement in GSP at 4 weeks over baseline between subjects randomized to treatment as compared to sham

Subjects Included in Analysis: All FAS subjects will be included in the analysis.

Endpoint(s): HDSS at follow-up. GSP % change at follow-up compared to baseline. will be calculated as in **Section 11.2.3.4**

Statistical Analysis: The proportion of patients with an HDSS of 1 or 2 at 4 weeks of follow-up AND at least 50% improvement in GSP at 4 weeks over baseline will be compared between treatment vs. sham using the Cochran-Mantel-Haenszel (CMH) test stratified by baseline HDSS value of 3 vs. 4 in the FAS population. Statistical significance is achieved with two-sided p-value <0.05 equivalent to one-sided p-value < 0.025. This analysis will be completed in the PP group as well.

11.3.3 To compare the proportion of patients with HDSS 1 or 2 at 4 weeks AND at least 75% improvement in GSP at 4 weeks over baseline between subjects randomized to treatment as compared to sham

Subjects Included in Analysis: All FAS subjects will be included in the analysis.

Endpoint(s): HDSS at follow-up. GSP % change at follow-up compared to baseline. will be calculated as in Section 11.2.3.4

Statistical Analysis: The proportion of patients with an HDSS of 1 or 2 at 4 weeks of follow-up AND 75% improvement in GSP at 4 weeks over baseline will be compared between treatment vs. sham using the Cochran-Mantel-Haenszel (CMH) test stratified by baseline HDSS value of 3 vs. 4 in the FAS population. Statistical significance is achieved with two-sided p-value <0.05 equivalent to one-sided p-value < 0.025. This analysis will be completed in the PP group as well.

11.3.4 To compare the duration of efficacy between subjects randomized to treatment as compared to sham

Subjects Included in Analysis: All FAS subjects will be included in the analysis.

Endpoint(s): HDSS

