Statistical Analysis: A Kaplan-Meier product limit method will be used for the analysis. Time 0 will be the treatment date. For subjects who do not respond to treatment, the duration of treatment will be 0. For subjects who do respond to treatment, the event is the first subsequent week of follow-up after the 4 week follow-up in which the subject reported an HDSS of 3 or 4 or censoring from the study either due to drop-out or completing the study without reverting to HDSS 3 or 4. The study groups will be compared using the Log-Rank statistic stratified by HDSS 3 or 4 at baseline.

This analysis will be completed for reversion to the patient's baseline value and in the PP group as well.

11.3.5 To compare mean change from baseline at 4 weeks in GSP between subjects randomized to treatment as compared to sham.

Subjects Included in Analysis: All FAS subjects will be included in the analysis.

Endpoint(s): The average of 2 accurate GSP measurements will be conducted for each Axilla at each time point. The total sweat production at each timepoint will be calculated by summing the average sweat production from both axilla. The change in GSP at 4 weeks will be calculated by subtracting the total sweat production at baseline from the total value at 4 weeks.

Statistical Analysis: An analysis of variance model will be used to compare average change in total GSP at 4 weeks as compared to baseline between randomized groups. The dependent variable is change in total GSP at 4 weeks as compared to baseline with independent variables to include randomized group, baseline HDSS, and two-way interaction terms.

A hierarchical stepwise backward elimination technique will be used to reduce the model. The two-way interactions will be reviewed first, the two-way interaction with the largest p-value provided that p-value is greater than 0.05 will be removed from the model and the model refit and repeated until only two-way interactions with p-values < 0.05 are retained. The main effects for any two-way interaction retained in the model must remain in the model as well as the randomized treatment. That being said, the main effects will be evaluated in the same manner as the two-way interaction terms. This analysis will be repeated in the PP population.

11.3.6 To compare responses to additional QOL questions from baseline throughout follow-up, as appropriate between subjects randomized to treatment as compared to sham.

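### Secondary endpoint 4 tests the GSP responder rate in the active arm against zero: one responder is enough to pass, and the sham arm plays no part

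*SAP*

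**What the plan says.** Protocol 9.10.2.2 and SAP 11.2.2 place this endpoint fourth and last in the fixed sequence. It is restricted to subjects randomised to N-SWEAT. The null hypothesis is that the proportion "is not statistically significantly different from 0", with success at the two-sided 0.05 level. The same paragraph adds: "It is expected that at least 50% of subjects will have at least 50% improvement in gravimetric sweat production". That 50% is an expectation only; it is neither the null value nor a performance goal.

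The decision rule is in Protocol 9.10.2.3.4 and SAP 11.2.3.4: the proportion is "statistically compared to zero by calculating the Wilson's 95% two-sided confidence interval and comparing the lower bound to zero". The protocol interprets a pass as follows: "If the lower bound is greater than zero, there is statistically significant evidence that the proportion of subjects with a clinically relevant improvement exists".

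The verdict has a use. Under SAP 11.2.1, if the primary endpoint is significant, "additional secondary endpoints will be evaluated for inclusion in the labeling for the device including p-values and 95% confidence intervals".

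GSP is compared with sham elsewhere, but only among the observational endpoints. SAP 11.3.2 and 11.3.3 test composites of HDSS and GSP response; in 11.3.2, HDSS 1 or 2 together with "at least 50% improvement in GSP at 4 weeks over baseline will be compared between treatment vs. sham using the Cochran-Mantel-Haenszel (CMH) test". SAP 11.3.5 compares mean change: "An analysis of variance model will be used to compare average change in total GSP at 4 weeks". For all of these, SAP 11.3 says that labelling data "will not include 95% confidence intervals or p-values".

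**The concern.** Protocol section 5 aims to show less sweating relative to sham-treated controls. GSP is the trial's direct measurement of sweat, but the gated sequence never compares it with sham. Two separate faults follow.

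- **The benchmark is empty.** A single responder refutes a null of exactly zero. The type I error under that null is zero, but nobody doubts that some subject will show a 50% fall.
- **The control arm is omitted.** Whatever null value is chosen, a test in one arm cannot separate a device effect from sham response, regression to the mean or differences in room conditions. Regression to the mean is a real possibility because subjects must exceed a GSP threshold to enter. SAP 11.2.3.4 itself lists temperature, humidity, position and time of evaluation as potential confounders.

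The sponsor's pilot (Protocol 3.3) shows why this matters: sham GSP fell by a mean of 44% and a median of 46%, and 14% of sham subjects reached the 50% threshold.

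At stake is a labelling claim. If the primary and secondaries 1 to 3 all succeed, a patch that improves HDSS and quality of life but does nothing to GSP beyond sham would very probably also gain a statistically significant sweat-reduction result.

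**Working it through.** **Inputs.** 50 evaluable subjects per arm and 55 randomised per arm (SAP 4 and 11.1); two-sided alpha 0.05 and an expected active rate of at least 50% (SAP 11.2.2); pilot sham rate 14% at 6 weeks, with 8 sham subjects treated (Protocol 3.3). I take n = 45 as a low case. Sham rates above 14% are my assumptions.

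**1. The plan's own sample size.** The documents give no power for GSP; the sample size is for the primary endpoint. With the usual formula, n = [1.96·√(2p̄(1−p̄)) + 0.8416·√(p₁(1−p₁)+p₂(1−p₂))]² / (p₁−p₂)²:

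- 85% vs 60%: 48.9, so 49 (plan: 50).
- 73% vs 44%: 44.1, so 45 (plan: 45).

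The plan's figures reproduce to within one subject, so 50 per arm is a fair basis for what follows.

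**2. When is the Wilson lower bound zero?** The bound is L = [p̂ + z²/2n − z·√(p̂(1−p̂)/n + z²/4n²)] / (1 + z²/n).

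- With no responders, p̂ = 0 and the numerator is z²/2n − z²/2n = 0.
- With any responder it is positive. For 1/50: (0.02 + 0.038415 − 1.96 × 0.027859) / 1.07683 = 0.0035.

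| Responders | Wilson 95% CI | Passes? |
|---|---|---|
| 0/50 | 0 to 7.1% | no |
| 1/45 | 0.39% to 11.6% | yes |
| 1/50 | 0.35% to 10.5% | yes |
| 1/55 | 0.32% to 9.6% | yes |

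**3. Chance of passing, given that step 4 is reached.** P(pass) = 1 − (1 − p)⁵⁰.

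| True active-arm rate | P(pass), n = 50 |
|---|---|
| 1% | 39.5% |
| 2% | 63.6% |
| 5% | 92.3% |
| 14% (pilot sham rate) | 99.95% |

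**4. How firm is the 14%?** It fits 1/7 = 14.3% better than 1/8 = 12.5%. The denominator is not stated, so 1/7 is an inference. The Wilson interval for 1/7 is 2.6% to 51%. Even at 2.6%, P(pass) = 1 − 0.974⁵⁰ = 73%.

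**5. A between-arm test for comparison.** I used the unstratified Mantel-Haenszel statistic z = (x_T − m/2)/√V, where m is total responders, N = 2n and V = n²m(N−m)/[N²(N−1)]. Success is z > 1.96 in favour of active.

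- Sham 7/50: active 16/50 gives z = 4.5/√4.472 = 2.13 (pass); 15/50 gives 4/√4.333 = 1.92 (fail). So 16/50 is needed.
- Sham 20/50: active 30/50 gives z = 5/√6.313 = 1.99 (pass); 29/50 gives 1.79 (fail). So 30/50 is needed.
- The present rule needs 1/50 in both cases.

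Full binomial enumeration at 50 per arm shows that a patch equal to sham would pass in 2.2% to 2.6% of trials for common rates of 5% to 40%. At 14% it is 2.4%, against 99.95% under the present rule.

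Power with 50% active response:

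| Sham rate | 50 per arm | 45 per arm |
|---|---|---|
| 14% | 98.1% | 96.8% |
| 20% | 89.5% | 85.9% |
| 25% | 74.5% | 68.6% |
| 30% | 54.6% | 47.6% |
| 40% | 18.2% | 14.5% |

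At 50 per arm, power is 80% at a sham rate of 23.4%. A simulated CMH test stratified by HDSS (200,000 replicates, HDSS 4 share assumed 30% or 50%, equal rates in both strata) agrees with the 50-per-arm column to within 0.2 percentage points.

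**The case against.** The strongest defence is that the endpoint claims little. Both documents title the objective as estimation and state openly that it covers the N-SWEAT arm only. The conclusion drawn is only that the proportion exceeds zero. Labelling is not automatic, and any p-value would travel with its interval, so a one-responder result would be seen as 0.35% to 10.5%. Sham GSP summaries from the observational analyses could also enter labelling by agreement with FDA. Several controls limit drift in GSP: qualification at both screening and baseline, exclusion if the readings differ by more than 100%, at least two readings per axilla, and similar room conditions and position.

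Part of this stands. It is a disclosed weak benchmark, not a contradiction. The controls reduce regression to the mean and room effects, though they do not remove them. The very high pass probability at 14% rests on a tiny pilot arm at a different time point.

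The defence does not rescue the test. Whatever the title says, SAP 11.2.2 gives the endpoint a null, an alternative and a success criterion, and SAP 11.2.1 gives it a route to labelling. The sham comparisons in 11.3.2, 11.3.3 and 11.3.5 are unadjusted for multiplicity and kept out of labelling inference. None of them tests the GSP responder rate alone.

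**Conclusion.** The concern holds. As written, step 4 is passed by one responder in about 50, and its verdict carries no information on patch versus sham. The one-responder result is algebraic and needs no assumption. The 99.95% figure assumes that step 4 is reached, 50 evaluable active subjects and a true active rate equal to the pilot's 14%; at the lower limit of that pilot estimate it is about 73%.

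The damage is confined to this endpoint and any claim built on it. It is last in the sequence, so no later test depends on it, and study success is unaffected. The active-arm rate and its interval remain useful as description. The plan should be changed, but the flaw does not threaten the trial.

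**What to change.** Replace hypothesis 4 with H₀: p_T ≤ p_S for a fall of at least 50% in total GSP at week 4. Test it between the randomised arms with the CMH test stratified by baseline HDSS, as SAP 11.3.2 already does for the composite. Keep the active-arm rate and its Wilson interval as description.

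- **Where:** Protocol 9.10.2.2 and 9.10.2.3.4; SAP 11.2.2 and 11.2.3.4. The synopsis and Protocol 6.3 also define the endpoint as active-arm only and must be changed to match.
- **When:** before the week-4 analysis, when the sponsor is unblinded (SAP 7).
- **Outliers:** SAP 11.2.3.4 allows outlying GSP values to be excluded. In a between-arm test, such exclusions should follow a rule applied blind and identically in both arms.
- **Alternative:** if the sponsor finds the power too low, take endpoint 4 out of the gated list and report both arms' rates descriptively.

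**Cost.** No new data are needed, because sham GSP is already collected. A protocol and SAP amendment is required, submitted to FDA and the IRB, with any necessary approvals in writing first (Protocol 12.5). The endpoint could then fail, and it would be underpowered if sham response exceeds about 23%. The pilot sham median fall of 46% lies close to the 50% cut-off, so a rate that high is plausible. Failure at this step would block no other test.
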